5.3 Participant Compensation

Participants can earn up to \$250 if they complete all available procedures in this study:

\$ 45.00
\$ 80.00
\$125.00
\$250.00

Participants found to be ineligible after the assessment will be compensated a total of \$20 for their time. They will be paid either by gift card or check upon completion of the study. Participants who leave the study before completing all visits will be paid for time.

5.4 Time and Events Table

		Session 1	Session 2	Session 3	Follow up Phone call
Procedure	Pre- Screen	Screening & Assessment	Week 1	Week 2	Week 6
Phone Interview	X				
Informed consent		X			
Pregnancy Screen Attestation		X ¹	\mathbf{X}^{1}	\mathbf{X}^{1}	
Demographics/Med History		X	X	Х	
Concomitant Meds		X	X	X	
MIRECC GAF		X			
SCID-IV (substance use module only)		Х			
YMRS		X	Х	Х	
HAM-D		X	Х	X	
C-SSRS		X	Χ	X	
BDI		X	X	X	
ASRM		X	Χ	Х	
PSWQ		X	Х	Х	
BIS		X			
BIS/BAS Scale		X			
Pregnancy Urine Test		X ²	X ²	X ²	
Urine Drug Screen		X ³	X ³	X ³	
Randomization		X			
EEG		X ⁴	X ⁴	X ⁴	
tACS			X^4	X ⁴	
Stimulation Side Effects Questionnaire			Х	Х	X
Adverse Events Assessment					X

X¹- Optional if agree to pregnancy test

X²- Required if attestation is not signed

X³- Required if indicated by verbal report

X⁴- Emotion Go-NoGo Task

6.0 ADVERSE EVENTS

6.1 Adverse Event Reporting Requirements

Adverse event (AE) monitoring and reporting is a routine part of every clinical trial and is done to ensure the safety of subjects enrolled in the studies as well as those who will enroll in future studies using similar agents. Data on adverse events will be collected after Sessions 2 and 3 through 30 days after study completion. Any serious adverse event that occurs more than 30 days after the last study

Session and is considered related to the study procedure must also be reported. Serious Adverse Events (SAEs) will continue to be followed until:

- Resolution or the symptoms or signs that constitute the serious adverse event return to baseline.
- There is satisfactory explanation other than the study procedure for the changes observed; or
 Death.

The investigator is responsible for the detection, documentation, grading, and assignment of attribution of events meeting the criteria and definition of an AE or SAE. The definitions of AEs and SAEs are given below. It is the responsibility of the PI to ensure that all staff involved in the trial is familiar with the content of this section.

Any medical condition or laboratory abnormality with an onset date before initial study procedure is considered to be pre-existing in nature. Any known pre-existing conditions that are ongoing at time of study entry should be considered medical history.

All events meeting the criteria and definition of an AE or SAE, as defined in Section 6.2, occurring from the initial study procedure through 30 days following the last Session must be recorded as an adverse event in the subject's source documents and on the clinical research file (CRF) regardless of frequency, severity (grade) or assessed relationship to the study procedure.

In addition to new events, any increase in the frequency or severity (i.e., toxicity grade) of a preexisting condition that occurs after the subject begins study procedure is also considered an adverse event. Review of AE and SAE data will be performed and documented on a routine basis by the study team and the PI during weekly study meetings.

6.2 **Definitions**

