10.2	Eve	ent Windows, Missed Assessments, Missed Sessions and Protocol Deviation	
Repo	orting		19
11.0	REGU	JLATORY	19
11.1	Inst	itutional Review Board (IRB)	19
11.2	Sub	ject Information and Consent	19
12.0	REFE	RENCES	20

tACS Study (HUM00208557)

13.0	APPENDIX	. 2	2
------	----------	-----	---

Title	Enhancing Neural Synchrony and Affective Cognitive Control in Bipolar Disorder using Personalized Transcranial Alternating Current Stimulation (tACS)
Study Design	The randomized, double-blind, sham-controlled, cross-over study will involve three sessions. The first session will involve a clinical interview, questionnaires, and EEG recording during a computerized task. The second and third sessions will involve tACS brain stimulation (or placebo stimulation) during a computerized task and EEG recording.
Study Duration	Enrollment duration: 12 months Subject follow-up duration: 1 month Estimated duration until study completion: 12 months
Study Center(s)	Single center
Aims	Aim #1: Evaluate the feasibility and acceptance of tACS among bipolar patients. Aim #2: Estimate the preliminary effects of personalizedtACS on theta-gamma phase-amplitude coupling (PAC) and cognitive control behavior in bipolar disorder (BD).
Number of Subjects	30
Disease/condition	Bipolar Disorder
Inclusion/Exclusion Criteria	See Section 3.0 for a complete list of inclusion and exclusion criteria
Description of Study Intervention:	HD-tACS will be used to deliver current (active vs. sham) to the electrodes to generate tACS most closely approximate endogenous neural activity. Participants will be fitted using a montage consisting of 5-9 electrodes placed over the right frontal and temporal scalp.
Duration of Study	approximately 6 weeks
Statistical Methodology	Aim 1: We will compare the percentage of participants requesting to discontinue the session and the number of mild and severe adverse events reported during and following the tACS vs. sham procedure using Bayes factors (BF). Aim 2: EEG data preprocessing and spectral analyses will be conducted using custom MATLAB scripts and EEGLAB following
	the general methods described in 11 150 5 published work.

STUDY SYNOPSIS

STUDY SCHEMA

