Previous literature suggests that participants are sensitive to stimulation until the sensory neurons in the skin acclimate to the stimulation. Thus, we will use sham stimulation as an active control condition. We will inform our participants that they will sense the stimulation in the skin but will acclimate to the stimulation soon after it begins. They will be informed that they will receive two version of the stimulation, to facilitate blinding in case the participant does not acclimate to the stimulation. For sham, a genuine cross-frequency waveform will be delivered at maximum strength for 12 s, followed by a ramp-down. The ramp-up and ramp-down during the sham stimulation is designed to mimic the feeling of acclimation that is experienced with verum stimulation due to sensory adaptation. Published data from Consultant [name]'s lab indicate that this procedure provides sufficient participant blinding to the condition⁴.

6) Cognitive Control Task (Emotion Go-NoGo Task)

Participants will engage in an Emotion Go-NoGo task to activate affective cognitive control during the baseline EEG as well as the stimulation sessions. In this task, participants view facial images exhibiting different emotions (neutral, happy, sad, or angry). For each face (150 ms), they are to press a button within 1500 ms if the face expresses the target emotion (Go trials; 80%) and withhold the response if the face expresses the distractor emotion (NoGo trials; 20%); the pairing of target and distractor emotions vary across blocks. The task includes a total of 640 trials, divided into 8 blocks of 80 trials each. Half (4) of the blocks include original face images (Easy condition), and the other half (4) include visually degraded images (Difficult condition). The two difficulty conditions are presented in alternating order (counter-balanced across participants). Accuracy (particularly on NoGo trials) and reaction time (on Go trials) will be used to index cognitive control behavior as outcome measures. [*Note: the timing and trial parameters of the actual task may be modified slightly depending on initial testing results].

- 7) *Stimulation Side Effects Questionnaire*. Participants will complete this questionnaire regarding their experience following each stimulation session. They will also be asked to rate how much the stimulation improved cognitive performance as well as if they experienced any side effects (e.g., headache, neck pain, tingling).

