Pleasant vs Neutral), and a grand total of 600 trials. Performance feedback will be provided and the stimuli presentation time will be adjusted based on performance after each block (e.g., if performance is above 90%, a 40ms shorter presentation time will be used in the next block) to ensure adequate number of errors and consistency in performance across participants within each part. Actual presentation and interval time may differ slightly in implementation from that described above. Estimated to take ~40 minutes. This task is designed to assess error and response monitoring within emotional contexts, which has been shown to be different from monitoring in other contexts, such as emotionally neutral context using arrows. Accuracy and reaction time will be used to index cognitive control behavior as outcome measures. EEG recorded during the Emotional Flanker task will be used to assess neurological indicators of attention control. [*Note: the timing and trial parameters of the actual task may be modified slightly depending on initial testing results. In order to reduce subject burden, experimenters may shorten the task and drop the display of pictures (neutral and valenced), using simple arrow cues instead to indicate a right or left button press].

Follow-up Phone Call (~ 5-10 min)

Approximately 4 weeks (+/- \sim 7 days) following the completion of Session 3, research staff will call to administer the Stimulation Side Effect Questionnaire as a final safety check and evaluate for any other possible side effects.

Stopping Rules

If a participant reports intolerable discomfort during the tACS procedure, the session will be discontinued. Immediately after each stimulation session ends, participants will complete a tACS side effects questionnaire. A study team member will review the responses and will immediately consult the PI if a participant reports a high (3) to very high (4) rating for any of the side effects rated to be related to the stimulation (4=probable or 5=definite). Subjects may also be withdrawn by the investigator when continued participation would present an unacceptable risk (e.g., worsening symptoms, suicidal thoughts, etc.).

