6.4 Serious Adverse Event Reporting Guidelines

The PI must be notified within ONE business day of study team's knowledge of any event meeting the criteria and definition of a serious adverse event, regardless of attribution, occurring during the study or within 30 days of the last administration of the study related treatment/intervention.

The investigator must report all events meeting the criteria and definition of a serious adverse event as per the IRBMED reporting guidelines.

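### The only scheduled all-cause adverse event assessment is a call about 28 ± 7 days after Session 3, so it can fall before the 30-day window closes and comes after both crossover conditions

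*Combined protocol and SAP*

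**What the plan says.** Section 6.1 describes the AE period in two places. Early on it says "Data on adverse events will be collected after Sessions 2 and 3 through 30 days after study completion". Further down it requires that any event "occurring from the initial study procedure through 30 days following the last Session must be recorded as an adverse event", regardless of frequency, severity or relationship to the procedure. Between these, it adds that a related serious AE arising more than 30 days after the last Session must be reported as well. Section 6.4 sets the serious AE notification period as "occurring during the study or within 30 days of the last administration of the study related treatment/intervention".

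The term *study completion* is not defined for an individual participant. The synopsis uses it for the trial as a whole ("Estimated duration until study completion: 12 months") and gives subject follow-up as 1 month.

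In Section 5.4 the row "Adverse Events Assessment" has one mark, in the column for the follow-up call. Section 5.2 places that call approximately 4 weeks (± about 7 days) after Session 3: "following the completion of Session 3, research staff will call to administer the Stimulation Side Effect Questionnaire as a final safety check". Staff are also to ask on the call about other possible side effects. The Stimulation Side Effects Questionnaire is marked at Session 2, Session 3 and the call. Section 5.2 describes it as covering the stimulation experience and asking "if they experienced any side effects (e.g., headache, neck pain, tingling".

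For Aim 1, the synopsis plans to compare the "number of mild and severe adverse events reported during and following the tACS vs. sham procedure using Bayes factors (BF". Sections 2.0 and 7.0 instead compare discontinuation and side-effect severity.

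**The concern.** Section 6.2.1 defines an AE irrespective of causality, so Section 6.1 creates an all-cause recording duty that runs to day 30 after the last Session. The schedule should give staff an occasion to ask about such events at or after the end of that period, and another before the second condition is given. It marks neither.

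Two things follow. First, if the call is made before day 30, any event between the call and day 30 is recorded only if the participant reports it unprompted. Second, a general medical event that begins after Session 2 and is missed by the existing checks may first be asked about weeks later, when the participant has had both active and sham stimulation. Its link to one condition then depends on recalled onset. That matters only for the synopsis comparison of AE numbers by condition.

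**Working it through.** This is calendar arithmetic; no error-rate or sample-size formula applies.

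**Inputs**
- Session 3 at Week 2 and the call at Week 6 (Section 5.4).
- Call at 4 weeks ± about 7 days after Session 3 (Section 5.2).
- Recording window ends on day 30 after the last Session (Section 6.1).
- Sessions 2 and 3 about 1 week apart (Section 5.2).
- Session 1 to stimulation about 1 week, for some up to about 30 days (Section 10.2).

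**Plan's own figure.** Week 2 + 4 weeks = Week 6, which agrees with the table.

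**Permitted call days after Session 3.** 28 − 7 = 21 at the earliest, 28 nominal, 28 + 7 = 35 at the latest. The tolerance is itself approximate.

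**Shortfall to day 30** = max(30 − call day, 0):
- day 21: 30 − 21 = 9 days
- day 28: 30 − 28 = 2 days
- days 30-35: 0 days

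The range 21-35 holds 15 days. Of these, 9 (days 21-29) precede day 30 and 6 (days 30-35) do not. This counts permitted days and is not a probability, because the documents give no distribution of call dates.

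**Session 2 to the call**, at a 7-day gap between sessions: 7 + 21 = 28, 7 + 28 = 35 and 7 + 35 = 42 days.

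**Effect of the undefined end point.** If *study completion* means Session 3, the first sentence of Section 6.1 also ends on day 30 and the two statements agree. If it means the call, collection would run to day 21 + 30 = 51, 28 + 30 = 58 or 35 + 30 = 65, with no contact scheduled after the call. If it means the end of the trial, no participant-level date can be computed.

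**Effect of the start wording.** If *after Sessions 2 and 3* is the start of a window, it begins later than the other statement by the Session 1 to Session 2 interval: about 7 days, up to about 30. If it describes occasions for collecting data, the starts do not differ, but the table lacks the corresponding marks.

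**Exposure if each event were assigned to the most recent stimulation.** The first condition would have about 7 days at risk (Session 2 to Session 3) and the second about 30 (Session 3 to the end of the window). Raw counts on that basis would not be comparable within a participant.

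**After the proposed change.** A call on days 30-37 gives 37 − 30 + 1 = 8 permitted days, each with a shortfall of 0.

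**The case against.** The strongest reply is that Section 6.1 sets a duty to record events and nowhere promises active questioning up to day 30. An event after the call can still be recorded if the participant reports it, related serious AEs remain reportable after day 30, and AE data are reviewed weekly. The nominal shortfall is 2 days, after stimulation whose side effects the protocol describes as mild and short-lived. All of this stands and keeps the point small. It does not explain why the final check should be timed to fall before the window that it serves has closed.

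Existing coverage is also substantial. YMRS, HAM-D, C-SSRS, BDI, ASRM and PSWQ are repeated at Sessions 2 and 3 and are listed before the stimulation step. History and concomitant medications are marked at both sessions, and staff ask about medication changes and drug use before each visit. Mood change and suicidality, the events of most concern in this population, are therefore looked for before the second condition. What is left is mainly non-psychiatric events not attributed to stimulation. The questionnaire is not shown to be an all-cause query, and the content of the history form is not given.

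A reader might infer that Section 6.1 contradicts itself with two incompatible windows. The documents do not support that. The late serious AE rule directly after the first sentence is anchored to the last Session, and Section 6.4 to the last administration, so the same end point is the natural reading of *study completion*. The wording on Sessions 2 and 3 can mean when data are gathered. On that reading the fault is a mismatch between text and table. Likewise, the AE questionnaire named in Section 10.2 may simply be the side-effects form under another name, since the protocol names that form loosely elsewhere.

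**Conclusion.** The point holds and is minor. A site that follows the schedule exactly can make its last active AE contact about 2 days before the recording window ends, and up to about 9 days before at the earliest permitted call. The schedule also marks no all-cause AE query between the two crossover conditions, although Section 6.1 says AE data are collected after Sessions 2 and 3. *Study completion* is an ambiguity to be cleared up and not a demonstrated contradiction.

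Two stronger conclusions should not be drawn. AE coverage between Session 2 and the call is partial, not absent. The primary outcomes are not compromised: the side-effect severity outcome is taken at the end of the stimulation session, and the Section 7.0 analysis of Aim 1 uses that outcome and discontinuation. Only the AE count comparison in the synopsis is exposed.

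The day counts take the approximate call window at face value as days 21-35, and the Session 2 to call interval assumes the planned one-week gap. Rescheduling for medication changes or drug use would lengthen that interval.

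**What to change.** 1. In the first sentence of Section 6.1, replace *study completion* with *the last Session*, which matches the rest of that section and Section 6.4.
2. Set the follow-up call at days 30-37 after Session 3 in Sections 5.2 and 5.4.
3. Mark the AE assessment at Sessions 2 and 3, with an open all-cause query and onset date taken before stimulation at Session 3.
4. If AE counts are compared by condition as in the synopsis, count only events within an equal window after each stimulation session, for example the first 7 days, or up to the participant's own Session 2 to Session 3 gap. List all other AEs descriptively. Assessors need only record dates. The data analyst, who is already unblinded under Section 4.2, can map session to condition.

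The cost is a few words in the protocol and table and a few minutes at visits already planned. The call moves at least 2 days later than its current nominal date, and its window narrows from 15 days to 8. A call made after day 37 would be late but would still cover day 30. No visit is added, and the sample size and primary analyses do not change.

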6.2.1 Adverse Events

Adverse Event Definition

An adverse event (AE) is any untoward medical occurrence in a subject participating in an investigational study or protocol regardless of causality assessment. An adverse event can be an unfavorable and unintended sign (including an abnormal laboratory finding), symptom, syndrome or disease associated with or occurring during the use of an investigational product whether or not considered related to the investigational product.

6.2.2 Serious Adverse Event

The study will comply with IRB and FDA reporting requirements and guidelines for SAEs. An adverse event is considered "serious" if, in the view of the investigator, it results in any of the following outcomes:

- Death If death results from (progression of) the disease, the disease should be reported as event (SAE) itself.
- A life-threatening adverse event An adverse even is considered 'life-threatening' if

An adverse even is considered 'life-threatening' if, in the view of either the investigator [or sponsor], its occurrence places the subject at immediate risk of death. It does not include an adverse event that, had it occurred in a more severe form, might have caused death.

- Inpatient hospitalization or prolongation of existing hospitalization for > 24 hours.
- A persistent or significant incapacity or substantial disruption of the ability to conduct normal life functions
- A congenital anomaly/birth defect
- Important medical event

Any event that may not result in death, be life-threatening, or require hospitalization may be considered serious when, based upon appropriate medical judgment, it may jeopardize the subject and may require medical or surgical intervention to prevent one of the outcomes listed in this definition of "Serious Adverse Event." Examples of such medical events include allergic bronchospasm requiring intensive treatment in an emergency room or at home; convulsions that do not result in inpatient hospitalization or the development of drug dependency or drug abuse.

Previously planned (prior to signing the informed consent form) surgeries should not be reported as SAEs unless the underlying medical condition has worsened during the course of the study. Preplanned hospitalizations or procedures for preexisting conditions that are already recorded in the subject's medical history at the time of study enrollment should not be considered SAEs. Hospitalization or prolongation of hospitalization without a precipitating clinical AE (for example, for the administration of study therapy or other protocol-required procedure) should not be considered SAEs. However, if the preexisting condition worsened during the course of the study, it should be reported as an SAE.

6.2.3 Expected Adverse Events

An adverse event (AE) is considered "expected" in clinical research studies, information on expected adverse events is summarized in the protocol and in the consent document.

6.2.4 Unexpected Adverse Event

An adverse event (AE) is considered "unexpected" if the event is not listed at the specificity or severity that has been observed.

6.3 Adverse Event Characteristics

6.3.1 Terms and Grading

The severity or grade of an adverse event may be measured using the following definitions:

Mild: Noticeable to the subject, but does not interfere with subject's expected daily activities, usually does not require additional therapy or intervention, dose reduction, or discontinuation of the study.

Moderate: Interferes with the subject's expected daily activities, may require some additional therapy or intervention but does not require discontinuation of the study.

Severe: Extremely limits to the subject's daily activities and may require discontinuation of study therapy, and/or additional treatment or intervention to resolve and may be life-threatening of fatal.

